3.2 Collaborator(s)/External partner(s)/Committee(s)

CCI [redacted]	Consultant Urologist	CCI [redacted] [redacted] [redacted]	Principle Investigator
----------------	----------------------	--	------------------------

CCI [redacted]	Senior Researcher	CCI [redacted] [redacted]	Senior statistician

4. Abstract

Acronym/Title	PRostAte Cancer vTe In SwEden: epidemiology and anticoagulation treatment of VTE PRACTISE
Protocol version and date	1.0, 12 May 2019
IMPACT study number	20653
Study type / Study phase	Observational, Phase IV
Author	CCI
Rationale and background	
Patients with cancer are at a significantly increased risk of experiencing a venous thromboembolism (VTE). VTE is defined by deep vein thrombosis (DVT) or pulmonary embolism (PE) and is a leading cause of morbidity and death among cancer patients. A variety of anti-coagulants are available to treat VTE with treatments differing between cancer and non-cancer patients. The use of such treatments has changed over time with a shift towards the increased use of non-vitamin K oral anticoagulants (NOACs) due to their ease of administration.
 
An increasing success of cancer treatments results in significant extension of survival, even in cases of metastatic diseases; therefore prevention of debilitating thrombotic events in these patients is gaining importance. Although prostate cancer (PCa) belongs to the cancer types with a relatively low risk of VTE, the burden of patients with PCa is high (the commonest cancer type in men); thus adequate treatment and secondary prophylaxis of VTE in this population is of clinical and public health importance.

Research question and objectives	
This study aims to identify the current landscape of VTE events and its treatment in prostate cancer (PCa) patients in Sweden.
 
The objectives include:
 
Primary objective
 
Among all men with PCa:
 
 1. To describe socio-demographic and clinical characteristics at the date of an incident PCa diagnosis. 2. To estimate the occurrence of cancer-related VTE. 3. To describe the cancer therapies in PCa at the initial

	
time after diagnosis.
 
Among men with PCa and a first cancer-related VTE event:
 
 4. To characterize the long-term anticoagulation treatment including choice of drug and duration of treatment. 5. To estimate the occurrence of recurrent VTE events by long-term anticoagulation treatment (LMWH, VKA or NOACs) and its estimated duration (up 3 months, 3-6 months, more than 6 months). 6. To determine the time between a first cancer-related and a recurrent VTE event. 7. To estimate the occurrence of post-VTE bleeding events leading to hospitalization, and mortality by anticoagulation treatment. 
Secondary objectives
 
Among PCa-free men from the general population:
 
 8. To describe socio- demographic and clinical characteristics at the date of inclusion into the database. 9. To estimate the occurrence of VTE events.
Study design	
This is a retrospective cohort study based on an existing on-going registry of men with PCa and randomly selected men without PCa in Sweden.

Population	
Included in this study will be all men with newly diagnosed PCa between 2007 -2016 as well as PCa-free men who have been frequency-matched to incident cases of PCa by birth year and county of residence.

Variables	
Variables include characteristics of PCa and (where possible) PCa-free men related to socio-demographic and clinical parameters such as comorbidities, cancer-specific characteristics and therapies including anticoagulation therapies. Outcomes of interest include:
 
In men with PCa: 1. DVT or PE; 2. Bleeding events leading to hospitalization; 3. Mortality.
 
In PCa-free men: 4. DVT or PE.

Data sources	
This study will use data from a research database, PCBaSe, which is a comprehensive database from Sweden encompassing information from over 180,000 prostate cancer patients identified from the national Cancer register and around 900,000 PCa-free men from the general population of Sweden (frequency matched on birth year and county) and selected

	from national population registers.
Study size	The full PCBaSe database contains data on 185 729 men diagnosed with PCa since 1998 and more than 900 000 PCa-free men. This study will utilize the period from 2007 and contain approximately 98 000 men with PCa and 500 000 PCa-free control men.
Data analysis	
Among men with PCa:
 
Descriptive statistics will be used to define the socio-demographic and clinical characteristics of all PCa patients at the date of incident PCa diagnosis (baseline) as well as main types of cancer therapies.
 
The occurrence (incidence rate) of cancer-related VTE events, split into PE and DVT events will be also described by Kaplan-Meier curves in different strata.
 
The anticoagulation (AC) treatment received by the PCa patients after the first cancer-related VTE event at an out-patient long-term basis will be reported by type of anticoagulation (LMWH, VKAs and NOACs) and its estimated duration (up to 3 months, 3-6 months, more than 6 months). Among this sub-group of patients, the occurrence (incidence rates) of recurrent VTE and the time to recurrence, post-VTE bleeding leading to hospitalisation, and mortality will be calculated by the type and duration of AC treatment.
 
Among PCa-free men:
 
Descriptive statistics will be used to define the socio-demographic and clinical characteristics of PCa-free men at the time of inclusion in PCBaSe (baseline).
 
The occurrence of VTE events, split into PE and DVT events will be also described by Kaplan-Meier curves in different strata.

Milestones	The project is planned to begin in May 2019 and will end in April 2020.

5. Amendments

<None>

6. Milestones

Table 1: Milestones

Milestone	Planned date
Study start	May 2019
Submission of application form for approval from Research Ethics Board Uppsala	March 2019
Development of a study file containing the data	June 2019
Upload study file Research Platform	June 2019
Registration in the EU PAS register	April 2019
Study end	December 2019
Final report of study results	April 2020

7. Rationale and background

Venous thromboembolism (VTE), including pulmonary embolism (PE) and deep vein thrombosis (DVT), is a leading cause of morbidity and death for cancer patients. Approximately 20% of all VTE cases occur in patients with cancer and more than 20% of patients with cancer will experience VTE (1). There is some evidence that that patients with both cancer and VTE were at a four times increased risk of developing recurrent thromboembolic complications and twice as likely to develop major bleeding during anticoagulant (AC) treatment than those without cancer. This risk varies during the course of the disease with the highest risk immediately after the initiation of chemotherapy (2). Risk factors for developing VTE in cancer patients is multifold and is determined by patient-related, tumor-related, cancer treatment - related and biomarker-related factors. Hence, the population of cancer patients as well as the choice of cancer treatment is highly heterogeneous (3); patients' individual responses to cancer treatment are highly variable often prompting physicians to make tailored decisions regarding the choice of an anticoagulant and the duration of therapy.

Low-molecular-weight heparin (LMWH) is the standard initial treatment for cancer-associated VTE (CAT) (4). For long term treatment, a vitamin K antagonist (VKA), warfarin, is the recommended treatment for several types of cancer including prostate, lung and breast cancers (5). More recently, the role of non-vitamin K oral anticoagulant agents (NOACs) is being assessed in several clinical trials. As the risk of thrombotic event depends on the 'cancer activity' that is variable in different

cancers, no reliable data are available on the risk-benefit balance of the anticoagulation therapy extended beyond 6 months in cancer patients.

An increasing success of cancer treatments results in significant extension of survival, even in cases of metastatic diseases; therefore prevention of debilitating thrombotic events in these patients is gaining importance. Although prostate cancer (PCa) belongs to the cancer types with a relatively low risk of VTE, the burden of patients with PCa is high; thus adequate treatment and secondary prophylaxis of VTE in this population is of clinical and public health importance.

A recent retrospective study analyzing the data from a large US administrative database showed that the majority of prostate cancer patients received warfarin for VTE treatment with an equal proportions of patients receiving LMWH and NOACs, of which rivaroxaban was mostly common. Reduced hazard of bleeding for NOACs versus warfarin and for NOACs versus LMWH was observed (6). An analysis of RIETE Registry showed a relatively low risk of bleeding but a substantial rate of VTE recurrences in PCa patients (7); however the patients' sample was limited and geographically diverse due to the nature of the Registry.

Rivaroxaban (Xarelto) is indicated for the treatment of DVT, PE and prevention of recurrence; its label that does not have a warning regarding its use in patients with active cancer. Demonstrating opportunities for use of oral anticoagulants such as rivaroxaban in cancer patients is thus essential.

The on-going 'Cancer Associated thrombosis – expLoring soLutions for patients through Treatment and Prevention with RivarOxaban' (CALLISTO) programme encompasses several initiatives, including both clinical trials as well as non-interventional studies and a survey. Nevertheless, several gaps in knowledge remain as some of the research questions will not be feasible to answer within the planned activities. Real-life data reflecting current practice are needed to address those gaps. In particular, there is a need to describe:

- Clinical characterization (staging, presence of metastasis, types of cancer therapy etc.) of cancer patients with an emphasize on most common cancers (prostate, lung, breast, colorectal etc.) in order to understand risk of thrombotic and bleeding events in this population.
- AC treatment of patients with cancer experiencing an acute VTE event, its duration, dose variation and switching against the background of different cancer treatment in order to understand prescription patterns of clinicians.
- Risk of recurrent thrombotic and bleeding events after the initiation of different AC therapies.

Non-interventional observational research data originating from cancer cohorts can provide relevant real-world clinical evidence and would be important complementing data from RCT's . As cancer patients are very heterogeneous in their clinical characteristics, it would be extremely difficult to construct a trial addressing all questions of interest; hence an observational study design based on data from clinical practice will provide a deeper understanding the consequences of current clinical practice for anticoagulation approaches in treatment of cancer patients and how the choice of a regimen influences risk of thrombotic and bleeding events. Generated evidence will support physicians in their treatment decisions.

Sweden offers a unique opportunity to study routine clinical practice and associated outcomes in cancer patients as notification of cancer has been mandatory in all Nordic countries for decades, and the Swedish Cancer Registry was established already in 1958. The completeness of data on incident cases is considered to be very high.

The study will focus on prostate cancer (PCa), the most common cancer form in men. It will be based on the data from the Prostate Cancer Database Sweden (PCBaSe), containing information from many national registries other than the Cancer register, such as Patient register, Dispensed drug register, Cause of Death registry and Population registries. In total, over 180,000 newly diagnosed cases of PCa in Sweden between 1996 to 2017 (currently available) together with a random sample of about 900,000 men from the general population without PCa in the same age group and area of residence as prostate cancer cases, are included into the PCBaSe.

8. Research questions and objectives

This study aims to identify the current landscape of VTE events and its treatment in prostate cancer (PCa) patients in Sweden.

8.1 Primary objective

Among all men with PCa:

- To describe socio-demographic and clinical characteristics at the date of an incident PCa diagnosis.
- To estimate the occurrence of cancer-related VTE.
- To describe the cancer therapies in PCa at the initial time after diagnosis.

Among men with PCa and a first cancer-related VTE event:

- To characterize the long-term anticoagulation treatment including choice of drug and duration of treatment.
- To estimate the occurrence of recurrent VTE events by long-term anticoagulation treatment (LMWH, VKA or NOAC) and its estimated duration (up 3 months, 3-6 months, more than 6 months).
- To determine the time between a first cancer-related and a recurrent VTE event.
- To estimate the incidence rates of post-VTE bleeding events leading to hospitalization, and mortality by anticoagulation treatment.

8.2 Secondary objectives

Among PCa-free men from the general population:

[figure not shown]
- To describe socio- demographic and clinical characteristics at the time of inclusion into the database.
- To estimate the occurrence of VTE events.

9. Research methods

Overview of study methodology and the process through which the study cohort will be selected is outlined in Figure 1.

Figure 1. Overview of study methodology

9.1 Study design

This is a retrospective cohort study based on on-going registry of men with PCa as well as men without PCa (PCa-free men) in Sweden.

9.2 Setting

9.2.1 Study population

The population will be selected from the PCBaSe 4.0 database that contains patients with PCa as well as PCa-free men from the general population in Sweden who have been frequency-matched to incident cases of PCa by birth year and county of residence. A sub-population will include PCa patients with a cancer-related VTE event (8).

9.2.2 Study time frame

The study will capture the observation period of 2007-2016, hence focusing on the period when the Prescribed Drug Registry became available.

9.2.3 Selection criteria from PCBaSe

PCa patients

Inclusion criteria

Initially all patients newly diagnosed with PCa between 2007-2016 with at least one year before the end of follow up date (31 December 2017) will be included.

From this population, a sub-population of PCa patients with a first cancer-related VTE event will be selected.

Exclusion criteria

No exclusions will be made.

Men without PCa

Inclusion criteria

All PCa-free men included in PCBaSe who are randomly selected from the general population of Sweden with the same birth year and county of residence of PCa patients diagnosed between 2007-2016.

Exclusion criteria

A PC free men diagnosed with a prostate cancer during the follow up will be identified and censored.

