9.2.4 Representativeness

The study cohort will include 98% of all newly diagnosed PCa patients in Sweden between 2007-2016 (8). PCBaSe contains information from multiple national health care registries such as The Patient Registry, The Prescribed Drug Registry, The Cause of Death Registry, The Registry of the Total Population and Population Changes, The Registries of Immigration and Emigration and The Longitudinal database on socioeconomic factors (LISA) with data on educational level, marital status, and income.

Included in the full dataset (starting from 1998) are PCa-free men selected from the general population of Sweden for every PCa incident case (in the ratio 1 PCa patient : 5 PCa-free men) who were frequency-matched on birth year and county of residence. To date, over 180,000 incident cases of PCa, together with 900,000 PCa-free men are included in the PCBaSe. Since all PCa and non-PCa patients have the same source of information on their clinical and demographic characteristics, comparisons can be made with consideration of these baseline characteristics between the populations.

This study consisting of all men with PCa and men without PCa in Sweden observed during 2007-2016 is clearly representative of treatment patterns and occurrences of outcomes of interest in Sweden during period of time.

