9.4 Follow up

9.4.1 Exposure to anticoagulants

The exposure to AC treatment will be defined in two ways:

- the first is by following the patients until the end of the follow-up time, regardless if they are still on the drug or not.
- the second way is to follow up the patients until the filled prescription for each respective drug expires (“on/treatment”).

A grace period of 90 days will be used to define a new prescription of anticoagulant. The duration of a prescription will be derived from the median number of days between consecutive respective prescriptions after the grace period has passed.

The treatment exposure can then be used to study the switching of treatments and the discontinuation of treatments.

A start date will be defined as the date of the dispensed prescription for patients receiving anticoagulation.

Patients will be censored at earliest date of:

- Time of first occurrence of a recurrent VTE event or a bleeding event (major bleeding event i.e. intracranial, gastrointestinal, urogenital bleeding, or other bleeding leading to hospitalisation) or death
 - Patients will be followed until occurrence of one of the above mentioned outcomes of interest; similarly, the analysis is repeated in the same way for the other outcomes of interest. Therefore, the patients were not censored at the first outcome of interest and outcomes on treatment after the first is also taken in to account. Only first-time events of the same type are considered.
- End of observation time (data lock point for the database at 31st October 2017)
- Treatment discontinuation
- Treatment switching patients who switched will be censored at the time of the date of a filled prescription from a pharmacy of the new drug.

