9.4.3 Discontinuation

It will not possible to determine exactly when an anticoagulant drug was discontinued from dispensing data, except when a switch was made, where the date for dispensing of the other drug was considered to mark the end of the exposure to the study drug.

Therefore, two fundamentally different methods will be used to approximate the time when exposure to the anticoagulant drug ended: a dispensed quantity based-method and a method based on refill intervals, which have both been evaluated in a previous study (9).

The dispensed quantity method counts the number of days the dispensed quantity of the drug would last if taken as prescribed and without missed doses. As the dosing of SOC varies greatly over time and between individuals, and the dosage is not recorded in the registers, this method could only be used for NOACs.

The refill interval method counts all days between two dispensings as days on treatment. If there is a gap exceeding six months, a single prescription or no more refills, treatment will be considered to have ceased three months after the last recorded dispensing. If there is another refill after more than six months, another treatment period will be considered to have started.

For both methods, the number of days on treatment days will be added up and a medicine possession ratio (MPR) calculated as the proportion of days on treatment out of the total number of days at risk (time to end of follow up, death or emigration). As a further sensitivity analysis, both methods will be assessed assuming that all patients were fully compliant to treatment (MPR 100%) and allowing

for patient's forgetfulness that every tenth dose is missed (on average). In this case a dispensed quantity would last approximately 11% longer than with full compliance.

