9.8 Data analysis

Descriptive statistics will be used to define the socio-demographic and clinical characteristics (including main types of cancer therapies) of all PCa patients at the time of PCa diagnosis (Objective 1 and 3) and PCa-free men at the time of inclusion in PCBaSe (Objective 8) and include variables of interest listed above.

All categorical variables will presented by counts and proportions and continuous variables by mean, standard deviation, range, median, and first and third quartiles.

The occurrence will be estimated by calculating an incidence rate (accompanied by 95% CI) of cancer-related VTE events, split into PE and DVT events, in men with PCa (Objective 2) and in PCa-free men (Objective 10). The incidence rate is defined as the number of events of interest divided by the total number of person-years at risk. In men with PCa, the person-time at risk will be calculated from date of incident PCa diagnosis up until an outcome of interest, death or end of follow-up, whichever came first. The occurrence will be also described by Kaplan-Meier curves in different strata within different time-periods.

The AC treatment received by the PCa patients after a first cancer-related VTE event on an out-patient long-term basis will be reported by type of anticoagulation (LMWH, VKAs and NOACs) and its estimated duration (from the time-point of a hospital discharge up to 3 months, 3-6 months, more than 6 months) (Objective 4).

Time at risk for Objectives 5, 6 and 7 (recurrent VTE, bleeding leading to hospitalisation or death) will be calculated from first cancer-related VTE (the time-frame of defining cancer-relatedness will be specified later) for each events of interest up until event, death or end of follow-up.

The 95% CI for the incidence rate will be calculated using the Poisson distribution.

Incidence rates of recurrent VTE, bleedings and death will be calculated by the type and duration of AC treatment (stratification variables); however no comparative analysis of outcomes in three sub-groups of AC treatments, is planned.

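### The protocol gives two different dates for the end of follow-up (31 December and 31 October 2017), and the person-time rule in 9.8 gives none, so rates could include up to 61 days per man in which no event can be recorded

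*Protocol*

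**What the plan says.** Protocol 9.2.3 admits "Initially all patients newly diagnosed with PCa between 2007-2016". The same sentence then sets a minimum of potential follow-up, so that only men "with at least one year before the end of follow up date (31 December 2017) will be included". It makes no exclusions among men with prostate cancer.

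Protocol 9.4.1 lists the censoring events for anticoagulant exposure. One of them is "End of observation time (data lock point for the database at 31st October 2017").

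Protocol 9.8 sets the rate: "The incidence rate is defined as the number of events of interest divided by the total number of person-years at risk". For VTE in men with prostate cancer, time runs from diagnosis "up until an outcome of interest, death or end of follow-up, whichever came first". The rule for Objectives 5 to 7 also stops at the end of follow-up. Neither sentence gives a date, and 9.8 has no separate person-time rule for the prostate-cancer-free men.

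Two neighbouring statements matter less. Section 9.2.2 says "The study will capture the observation period of 2007-2016", and 9.2.4 speaks of "all men with PCa and men without PCa in Sweden observed during 2007-2016". Section 9.4.3 computes the medicine possession ratio over "time to end of follow up, death or emigration", whereas the censoring list in 9.4.1 and the person-time rules in 9.8 do not mention emigration.

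**The concern.** Every incidence rate in the study needs a closing date for its denominator. The only place that attaches a date to the end of follow-up as such is 9.2.3, so a programmer who follows 9.2.3 and 9.8 literally would close person-time on 31 December 2017. The October date stands in the exposure section, but the protocol describes it as the lock of the database, so it limits event capture for every objective. The last two months would then add to the denominator and nothing to the numerator, and the same men would stay in the Kaplan-Meier risk sets with no chance of an event. Rates would be too low, most of all in men with short, recent follow-up.

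The choice of date also decides whether the latest diagnoses satisfy the one-year requirement, and so who is in the cohort.

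**Working it through.** **Inputs from the protocol.** Diagnosis window 1 January 2007 to 31 December 2016, which is 3,653 days (9.2.3). End dates 31 December 2017 (9.2.3) and 31 October 2017 (9.4.1). About 98,000 men with prostate cancer and 500,000 without (9.6).

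**Assumptions, not in the protocol.** Diagnoses are uniform over the window. The death rate m is constant, from 0 to 10 per 100 person-years. Time lost after a VTE is ignored.

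**1. The plan's own one-year clause.** From 31 December 2016 to 31 December 2017 is 365 days. The clause therefore holds for every diagnosis in the window under the date given beside it.

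**2. The same clause under the lock date.** From 31 December 2016 to 31 October 2017 is 304 days. The last diagnosis date with 365 days is 31 October 2016. Diagnoses from 1 November to 31 December 2016 cover 61 days: 98,000 × 61/3,653 ≈ 1,636 men, or 1.7%.

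**3. Upper limit of the empty time.** The gap from 31 October to 31 December 2017 is 61 days. With no deaths this is 98,000 × 61/365.25 ≈ 16,367 person-years in men with prostate cancer, and 500,000 × 61/365.25 ≈ 83,504 in the others.

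**4. Effect on the overall rate.** A man with potential follow-up t contributes on average (1 − exp(−m·t))/m person-years, or t if m = 0. Averaging over uniform diagnosis dates gives the table below. With the event count fixed, the ratio of October to December person-time is the factor by which the rate is too low.

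| Deaths per 100 PY | Mean PY to 31 Dec 2017 | Mean PY to 31 Oct 2017 | Empty PY, 98,000 men | Rate ratio |
|---|---|---|---|---|
| 0 | 5.999 | 5.832 | 16,367 | 0.9722 |
| 3 | 5.385 | 5.245 | 13,757 | 0.9739 |
| 5 | 5.028 | 4.902 | 12,304 | 0.9750 |
| 7 | 4.706 | 4.593 | 11,040 | 0.9761 |
| 10 | 4.279 | 4.183 | 9,441 | 0.9775 |

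The understatement is 2.3% to 2.8%.

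**5. Men diagnosed in 2016.** With no deaths, potential follow-up to 31 December 2017 runs from 730 down to 365 days, mean 547.5. To 31 October it runs from 669 to 304, mean 486.5. The ratio is 486.5/547.5 = 0.889. At 10 deaths per 100 person-years it is 0.896. The understatement is 10% to 11%.

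**6. Compared with the precision claimed.** In the 9.6 table, a cumulative incidence of 5% has an interval width of 0.28 points. The half-width is 0.14 points, which is 0.14/5 = 2.8% of the estimate. At 1% it is 0.06/1 = 6%. In relative terms, a 2-3% systematic error is about as large as the sampling error at 5% incidence, and about half of it or less at 1%.

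**The case against.** The strongest reply is that empty person-time is conditional. It arises only if someone counts time beyond the date that the protocol itself calls the database lock, and a careful analyst would not. That is fair. The point is that the text permits the error, not that the error will occur.

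Three stronger conclusions are tempting, and the protocol does not support them:

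- **That follow-up might end in 2016.** A reader might take 2007-2016 in 9.2.2 and 9.2.4 as a third end date; stopping at 31 December 2016 instead of 31 December 2017 would remove about 14-17% of person-time under the same assumptions. But 9.2.3 uses the same years for diagnosis, and both dates labelled as an end fall in 2017. The natural reading is a diagnosis window, loosely called an observation period.
- **That the error biases anticoagulant classes differently.** Use moved towards NOACs over time, so a reader might infer this. But 9.4.1, the section that governs anticoagulant exposure, already censors at 31 October 2017, and 9.8 plans no comparison of the classes. The inference is speculative.
- **That the one-year clause biases the rates.** The clause agrees with its own date. Under the October date the men affected still have about 10 to 12 months of potential follow-up, which person-year rates accommodate without bias. It is a mismatch of wording.

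Emigration is named in 9.4.3 only for the possession ratio, and a full list of censoring events may stand in a statistical analysis plan. It is a minor alignment and adds no weight here.

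**Conclusion.** The contradiction between 31 October and 31 December 2017 is explicit, and nothing in the protocol reconciles the two dates. Because 9.8 leaves its end of follow-up undated, a literal reading can put up to 61 event-free days per man into the rates of both cohorts. For men with prostate cancer the overall understatement would be about 2-3%, rising to about 10-11% for those diagnosed in 2016. These sizes rest on uniform diagnosis dates and death rates of 0 to 10 per 100 person-years, and on closing the denominator in December. If the lock date is used throughout, the rates are unaffected; what remains is that about 1.7% of men do not meet the one-year clause. This is a modest inconsistency that should be corrected because the correction is nearly free and the rates depend on the date.

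**What to change.** - State one end date and use it in 9.2.3, 9.4.1 and 9.8: the earliest date to which all linked registers are complete, which is 31 October 2017 if that is the lock.
- Apply it to both events and person-time, in men with and without prostate cancer.
- Either drop the one-year clause or restate the diagnosis cut-off so that it fits. With a 31 October 2017 end, the last qualifying diagnosis date is 31 October 2016.
- Say in 9.2.2 that 2007-2016 is the diagnosis window.
- As a minor alignment, add emigration to the censoring rules in 9.4.1 and 9.8. Section 9.2.4 shows that the migration registers are linked.

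The cost is wording, plus slightly less person-time than under the December date, or a cohort about 1.7% smaller if the one-year clause is kept and the cut-off moved.
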